## **13.8 Actiwatch**

An Actiwatch (Philips Respiration, Bend, Oregon, USA) will be used to measure sleep over 7 day at Visit 8a prior to the end of the study in both arms.

# **14 Data Analysis**

## **14.1 Primary Endpoint Analysis**

The primary analysis will evaluate the between group difference in time spent in the target glucose range from 3.9 to 10.0 mmol/l (70 to 180 mg/dl) based on CGM glucose levels during the four month intervention periods.

Mean  $\pm$  SD or summary statistics appropriate to the distribution will be reported for the primary endpoint over the four month period by treatment intervention. The treatment interventions will be compared using a linear mixed model adjusting for period as a fixed effect and site as a random effect. The model will account for correlated data from the same subject. A 95% confidence interval will be reported for the difference between the interventions based on the linear mixed model.

Residual values will be examined for an approximate normal distribution. If values are highly skewed, then a ranked normal score transformation will be used instead. However, previous experience suggests that the primary endpoint will follow an approximately normal distribution. A separate model will also be built with the inclusion

of a period by treatment interaction to assess for the presence of a carryover effect. A two-sided p-value will be reported.

The primary analysis will be a single statistical comparison of a single outcome measure. No formal corrections for multiple comparisons will be performed for the secondary analyses in this study.

The primary analysis will be performed on an intention-to-treat basis using the treatment order assigned by randomization. Only subjects with the minimum number of hours of CGM data as specified in the analysis plan will be included.

A per-protocol analysis restricted to participants with a minimum of 60% CGM data during control period and 60% use of closed-loop during closed-loop period will be conducted for the primary endpoint.

A detailed analysis plan will be provided separately.

#### *Primary endpoint hypotheses*

- *Null Hypothesis:* There is no difference in the true mean time spent in the target range (3.9 to 10.0 mmol/L) over the four month period between the two treatment groups.
- *Alternative Hypothesis:* There is a nonzero difference in the true mean time spent in the target range over the four month period between the two treatment groups.

## **14.2 Other Key Endpoints**

For the following key endpoints, the familywise type I error rate (FWER) will be controlled at two sided  $\alpha = 0.05$ . A gatekeeping strategy will be used, where the primary endpoint will be tested first, if passing the significance testing, other key endpoints will be tested in the order listed below using the fixed-sequence method at  $\alpha = 0.05$ .

- Time spent with sensor glucose levels between 3.9 to 10.0 mmol/l (70 to 180 mg/dl)
- Time spent above target glucose (10.0 mmol/l) (180 mg/dl)
- HbA1c
- Average of glucose levels
- Time spent below target glucose (3.9 mmol/l) (70 mg/dl)

## **14.3 Secondary Efficacy Analyses**

The following endpoints will be considered exploratory and Benjamini-Hochberg false discovery rate (FDR) adjusted p-values will be calculated within each subcategory below:

*CGM derived indices:*

- Standard deviation, and coefficient of variation of glucose levels
- Time with glucose levels <3.0 mmol/l (54 mg/dl)
- Time with glucose levels in significant hyperglycaemia (glucose levels > 16.7 mmol/l) (300 mg/dl)
- AUC of glucose below 3.5 mmol/l (63 mg/dl)

*Insulin and Other Endpoints:*

- BMI SDS
- Total, basal, and bolus insulin dose

For all secondary endpoints, summary statistics appropriate to the distribution will be tabulated by treatment group. Analysis of all secondary CGM and insulin endpoints will parallel the primary analysis. The models comparing BMI standard deviation score and HbA1c will also adjust for baseline value at the start of each period.

For BMI standard deviation score and HbA1c, a longitudinal model adjusting for period as a fixed effect will be constructed to compare treatment arms. The model will include two time points: (1) period 1 outcome, and (2) period 2 outcome.

A ranked normal score transformation will be applied to all highly skewed secondary endpoints.

Summary statistics for the following outcome metrics will also be tabulated separately for daytime (defined as 8am to less than 12am) and night time (defined as 12am to less than 8am) over the four month period:

- Percent time with glucose levels spent in the target range (3.9 to 10.0 mmol/L)
- Mean of glucose levels
- Standard deviation of glucose levels
- Percent time with glucose levels below 3.9 mmol/L
- Total insulin dose

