**Table 7 Glucose control during 24/7 closed loop and sensor augmented pump therapy over 12 weeks free-living home use in adults with type 1 diabetes (APHome04 study).**

	Closed loop (n=32)	Control (n=33)	P value
Time spent at glucose (%)	67.7 ± 10.6	56.8 ± 14.2	<0.001
3.9 to 10.0 mmol/l			
> 10 mmol/l	29.2 ± 11.4	38.9 ± 16.6	<0.001
< 3.9 mmol/l	2.9 (1.4, 4.5)	3.0 (1.8, 6.1)	0.02
Mean glucose (mmol/l)	8.7 ± 1.1	9.3 ± 1.6	<0.001
HbA1c (%)	7.3 ± 0.8	7.6 ± 1.1	0.002
Total daily insulin (U/day)	48.8 ± 16.1	48.1 ± 15.4	0.6

HbA1c, mean glucose and time spent above target range were significantly reduced during closed loop, while time spent below target was low and comparable during both interventions. Hypoglycaemia exposure measured by AUC <3.5 mmol/l was reduced during closed loop ( $p=0.004$ ). Reduction in mean glucose and time spent above target range during closed loop was brought about without changing the total daily insulin delivery ( $p=0.6$ ).

**KidsAP01.** In an open-label, multinational, randomised crossover study involving KidsAP Consortium we analysed data from 23 young children aged 1 to 7 years on insulin pump therapy (age 5 (3 to 6) years, median (IQR): median HbA1c  $7.4 \pm 0.7\%$ , mean $\pm$ SD: duration of diabetes  $3.1 \pm 1.7$  years) who underwent two 21-day periods of unrestricted living comparing CL with diluted insulin aspart (U20) and CL with standard strength insulin aspart (U100) in random order.

The proportion of time that sensor glucose was in the target range between 3.9 and 10mmol/l (primary endpoint) was similar between interventions ( $72 \pm 8\%$  vs.  $70 \pm 7\%$ ; CL with diluted U20 insulin vs. CL with standard strength U100 insulin;  $p=0.14$ ; Table 8).

[figure not shown]
**Table 8 Glucose control during 24/7 closed loop with diluted insulin aspart (U20) and CL with standard strength insulin aspart (U100) over two 21-day periods of free-living home use in 23 children with type 1 diabetes aged 1 to 7 years (KidsAP01 Study).**

	Diluted (n=23)	Non diluted (n=23)	P value
% Time in Range 3.9-10.0 mmol/L	$72\% \pm 8\%$	$70\% \pm 7\%$	0.14
% Time >10.0 mmol/L	$23\% \pm 9\%$	$25\% \pm 7\%$	0.21
% Time <3.9 mmol/L	$4.5\% \pm 1.7\%$	$4.7\% \pm 1.5\%$	0.46
Mean Glucose (mmol/L)	$8.0 \pm 0.8$	$8.2 \pm 0.6$	0.12
Total Insulin (U/day)	$17.3 \pm 5.6$	$18.4 \pm 6.6$	0.09

Data shown are mean  $\pm$  SD

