**Table 8 Schedule of study visits when closed loop intervention precedes sensor augmented pump therapy**

	Visit / contact	Description	Start relative to previous / next Visit / Activity	Duration	Comment
Consent and training	Visit 1	Recruitment visit: Consent/assent, HbA1c questionnaires	-	1-2 hours	
	Visit 2	CGM start: CGM training, initiation of CGM, competency assessment	Within 2 weeks of Visit 1 (may coincide with Visit 1)	2-3 hours	May be repeated if competency not achieved
	Visit 3	Pump start: insulin pump training, study pump initiation, competency assessment	Within 1 week of Visit 2 (may coincide with Visit 2)	2-4 hours	May be repeated if competency not achieved
Run-in 2-4 weeks	Contact 1	Review pump settings and CGM data; adjustment of treatment	After 1 week of visit 3 ( $\pm$ 3 days)	30 minutes	
	Visit 4*	End of run-in, adjustment of treatment, treatment adherence assessment	After 2-4 weeks of visit 3 (minimum of 2 weeks)	1 hour	Run-in and Visit 4 may be repeated if non-compliant
	Randomisation		Immediately after Visit 4		If compliant with pump & CGM use
CL Intervention 16 weeks	Visit 5	CL initiation: training (CL), competency assessment	Within 1 week of Visit 4	1-2 hours	
	Contact 2	Follow up after CL start	Within 24 to 48 hours after Visit 5	30 minutes	
	Contact 3	Follow up, review use of study devices	After 1 week of Visit 5 ( $\pm$ 3 days)	30 minutes	
	Contact 4	Follow up, review use of study devices	After 4 weeks of Visit 5 ( $\pm$ 2 weeks)	30 minutes	
	Contact 5	Follow up, review use of study devices	After 8 weeks of Visit 5 ( $\pm$ 2 weeks)	30 minutes	
	Contact 6	Follow up, review use of study devices	After 12 weeks of Visit 5 ( $\pm$ 2 weeks)	30 minutes	
	Visit 6	End of 1st study arm: device download, HbA1c, questionnaires, interview	After 16 weeks of Visit 5 ( $\pm$ 2 weeks)	< 1 hour	
WASHOUT PERIOD (1-4 WEEKS)					
Sensor augmented pump therapy 16 weeks	Visit 7	Sensor augmented pump therapy initiation: refresher training	After 1-4 weeks of Visit 6	1-2 hours	
	Contact 7	Follow up after Sensor augmented pump therapy start	within 24 to 48 hours after Visit 7	30 minutes	
	Contact 8	Follow up, review use of study devices	After 1 week of Visit 7 ( $\pm$ 3 days)	30 minutes	
	Contact 9	Follow up, review use of study devices	After 4 weeks of Visit 7 ( $\pm$ 2 weeks)	30 minutes	
	Contact 10	Follow up, review use of study devices	After 8 weeks of Visit 7 ( $\pm$ 2 weeks)	30 minutes	

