**Table 9 Schedule of study visits when sensor augmented pump therapy precedes closed loop intervention.**

	Visit / contact	Description	Start relative to previous / next Visit / Activity	Duration	Comment
Consent and training	Visit 1	Recruitment visit: Consent/assent, HbA1c, questionnaires	-	1-2 hours	
	Visit 2	CGM start: CGM training, initiation of CGM, competency assessment	Within 2 weeks of Visit 1 (may coincide with Visit 1)	2-3 hours	May be repeated if competency not achieved
	Visit 3	Pump start: insulin pump training, study pump initiation, competency assessment	Within 1 week of Visit 2 (may coincide with Visit 2)	2-4 hours	May be repeated if competency not achieved
Run-in 2-4 weeks	Contact 1	Review pump settings and CGM data; adjustment of treatment	After 1 week of visit 3 ( $\pm$ 3 days)	30 minutes	
	Visit 4*	End of run-in, adjustment of treatment, treatment adherence assessment	After 2-4 weeks of visit 3 (minimum of 2 weeks)	1 hour	Run-in and Visit 4 may be repeated if non-compliant
	Randomisation		Immediately after Visit 4		If compliant with pump & CGM use

Sensor augmented pump therapy 16 weeks	Visit 5	Sensor augmented pump therapy initiation: refresher training	Within 1 week of Visit 4	1-2 hours	
	Contact 2	Follow up after Sensor augmented pump therapy start	Within 24 to 48 hours after Visit 5	30 minutes	
	Contact 3	Follow up, review use of study devices	After 1 week of Visit 5 ( $\pm$ 3 days)	30 minutes	
	Contact 4	Follow up, review use of study devices	After 4 weeks of Visit 5 ( $\pm$ 2 weeks)	30 minutes	
	Contact 5	Follow up, review use of study devices	After 8 weeks of Visit 5 ( $\pm$ 2 weeks)	30 minutes	
	Contact 6	Follow up, review use of study devices	After 12 weeks of Visit 5 ( $\pm$ 2 weeks)	30 minutes	
	Visit 6	End of 1st study arm: device download, HbA1c, questionnaires, interview	After 16 weeks of Visit 5 ( $\pm$ 2 weeks)	<1 hour	
WASHOUT PERIOD (1-4 WEEKS)					
CL Intervention 16 weeks	Visit 7	CL initiation: training (CL), competency assessment	After 1-4 weeks of Visit 6	1-2 hours	
	Contact 7	Follow up after CL start	within 24 to 48 hours after Visit 7	30 minutes	
	Contact 8	Follow up, review use of study devices	After 1 week of Visit 7 ( $\pm$ 3 days)	30 minutes	
	Contact 9	Follow up, review use of study devices	After 4 weeks of Visit 7 ( $\pm$ 2 weeks)	30 minutes	

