## **9.11 Washout**

A one to four week washout period will follow when subjects/guardians could continue using the study pump and CGM (but not closed loop), or revert to their own insulin pump. Subjects will then cross over to the alternative intervention.

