# **12 Methods and Assessments**

## **12.1 Procedures**

### **12.1.1 Height and Weight**

These will be recorded at the study initiation visit at baseline and at the end of each study arm. Those participating in the extension phase will have height and weight recorded at 18 months after the primary phase final study visit. Height will be measured in centimetres using calibrated measuring devices. Weight will be measured in kilograms using a calibrated electronic scale.

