## **12.2 Laboratory Methods**

### **12.2.1 HbA1c**

A blood sample for the measurement of HbA1c levels will be taken at four different time points: baseline, at the end of each primary phase study arm, and at the end of the extension phase (UK sites only). HbA1c will be measured using an International Federation of Clinical Chemistry and Laboratory Medicine (IFCC) aligned method. All HbA1c testing must follow National Glycohemoglobin Standardization Program (NGSP) standards. Those participating in the extension phase will have local or point-of-care HbA1c measurements taken 3-monthly (UK sites only).

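### Protocol 14.3 and the SAP give different models for HbA1c and BMI SDS, and the protocol's start-of-period baseline has no scheduled measurement in period 2

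*Combined protocol and SAP*

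**What the plan says.** Protocol 14.3, on HbA1c and BMI SDS: "The models comparing BMI standard deviation score and HbA1c will also adjust for baseline value at the start of each period". It then describes a longitudinal model: "The model will include two time points: (1) period 1 outcome, and (2) period 2 outcome".

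SAP 7.4.3 (HbA1c) and 7.4.4 (BMI SDS) give the model three time points: baseline, period 1 and period 2. SAP 15.4 adds that both analyses follow the primary analysis. SAP 6.3 describes that analysis as three records per child, period as a fixed effect, site as a random effect, and baseline entered as an outcome record. It explains that period 2 has no baseline of its own and that adjusting for a post-randomisation one can bias the result.

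The measurement schedule is as follows.
- Height and weight (protocol 12.1.1): "These will be recorded at the study initiation visit at baseline and at the end of each study arm".
- HbA1c (protocol 12.2.1): "taken at four different time points: baseline, at the end of each primary phase study arm, and at the end of the extension phase".
- Visit 7, which opens period 2, is listed as "Sensor augmented pump therapy initiation: refresher training" in Table 8 and "CL initiation: training (CL), competency assessment" in Table 9.
- Between Visits 6 and 7 (protocol 9.11): "A one to four week washout period will follow".

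Protocol 14.2 and SAP 6.3 both place HbA1c third in the fixed sequence, ahead of mean glucose and time below 3.9 mmol/l.

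**The concern.** The two documents define different models for the same endpoint, and neither says which governs. The protocol's model also needs a covariate that the schedule does not supply for period 2. An analyst following 14.3 literally would probably use the Visit 6 value. That value is the period-1 outcome under the other treatment, so it differs between the two sequences by the treatment effect itself. Adjusting for it adds part of that effect back into the period-2 comparison.

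At stake are the HbA1c estimate and its confidence interval, and the clarity of a test that decides whether two further key endpoints are formally tested. BMI SDS is exploratory, so less depends on it.

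**Working it through.** **Is there a period-2 baseline?** In the primary phase, HbA1c, height and weight are scheduled at baseline, Visit 6 and Visit 8b. The repeat HbA1c in the synopsis, for screening more than 28 days before randomisation, precedes period 1 and does not help. Visit 6 is the only scheduled measurement near the start of period 2.

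**Size of the bias if Visit 6 is used.** Let τ be the closed-loop effect, β the slope on the period-start value, and c the share of τ carried into period 2.
- Period 1: the baseline is balanced by randomisation, so the contrast is τ.
- Period 2: the unadjusted contrast is τ − cτ. Children now on closed loop were on control at Visit 6, so their covariate differs by −τ. The adjusted contrast is τ − cτ − β(−τ) = τ(1 − c + β).
- Average over the two periods, protocol rule: estimate/true ≈ 1 + (β − c)/2.
- SAP model: estimate/true ≈ 1 − c/2.
- The gap is β/2 of the effect, whatever c is. If τ = 0, neither estimate is biased.

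**Inputs.** The documents give no planning figures for HbA1c. Protocol 4.3.2 says of the adult APHome04 trial that "HbA1c, mean glucose and time spent above target range were significantly reduced during closed loop". Its Table 7 shows 7.3 ± 0.8 versus 7.6 ± 1.1, p = 0.002. I take a difference of −0.3 and SD 0.8 (KidsAP01, in this age group, reports SD 0.7). Correlations of 0.3 to 0.9 are assumed. If Table 7's p-value comes from a paired test with n = 32, then t = 3.375, the SD of differences is 0.3 × √32 / 3.375 = 0.503, and the correlation is (0.64 + 1.21 − 0.253)/(2 × 0.8 × 1.1) = 0.907. Allowing for rounding of the difference, the range is 0.79 to 0.99.

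**Simulation.** n = 72, 36 per sequence, equal within-child correlation, REML, t with 70 df, 4,000 replicates per setting, no site effect. Monte Carlo error of estimate/true is at most 0.0075. Results with no carryover (RI = random intercept, CS = unconstrained compound symmetry):

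| Correlation | 0.3 | 0.5 | 0.7 | 0.8 | 0.9 |
|---|---|---|---|---|---|
| Estimate/true, 14.3 RI | 1.139 | 1.235 | 1.347 | 1.387 | 1.450 |
| Estimate/true, 14.3 CS | 1.189 | 1.300 | 1.402 | 1.427 | 1.471 |
| Estimate/true, SAP | 0.997 | 0.992 | 1.000 | 0.995 | 1.004 |
| 95% coverage, 14.3 RI | 0.934 | 0.892 | 0.783 | 0.686 | 0.412 |
| 95% coverage, 14.3 CS | 0.932 | 0.900 | 0.819 | 0.749 | 0.494 |
| Pass HbA1c step, 14.3 RI | 0.752 | 0.873 | 0.976 | 0.996 | 1.000 |
| Pass HbA1c step, 14.3 CS | 0.718 | 0.820 | 0.953 | 0.992 | 1.000 |
| Pass HbA1c step, SAP | 0.756 | 0.880 | 0.981 | 0.998 | 1.000 |

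SAP coverage is 0.946 to 0.957. With the fitted slopes, the formula gives 1.140, 1.246, 1.347, 1.396 and 1.445 for the RI row.

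**Carryover.** At 25%, estimate/true is 1.03 to 1.35 under 14.3 and about 0.88 under the SAP. At 50% it is 0.89 to 1.22 and about 0.75. The gap in HbA1c percentage points stays at 0.04–0.06, 0.10–0.12 and 0.13–0.14 for correlations 0.3, 0.7 and 0.9.

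**Zero effect.** Mean estimates are within 0.005 of zero. Rejection is 0.059 to 0.109 for 14.3 RI, 0.045 to 0.059 for 14.3 CS and 0.041 to 0.054 for the SAP, so any type I inflation depends on how 14.3 is fitted.

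**Cross-check.** A simpler simulation used least squares for 14.3 and generalised least squares with known covariance for the SAP model, with an effect of −0.5 SD and 600 runs. It gives ratios of 1.148, 1.252, 1.345 and 1.426 at correlations 0.3, 0.5, 0.7 and 0.85. The SAP model returns −0.50 throughout.

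**The case against.** Protocol 14.1 defers detail to a separate analysis plan. That plan states the model, explains why no period-2 baseline is used, and logs a clarification of these analyses in version 3.0. This stands as a reason for low severity. It does not remove the conflict: 14.3 still specifies a different model, and no precedence rule is given. SAP 3.0 is dated at the stage when initial analyses were complete, and the documents do not show what earlier SAP versions said about this model.

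The bias figures assume the Visit 6 value is used. Carrying the recruitment baseline into both periods of a two-record model would be unbiased without carryover (0.99, 1.01 and 1.00 at correlations 0.3, 0.7 and 0.9). That is correct, but it is not what 14.3 says, since 14.3 asks for the value at the start of each period.

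The largest figures depend on a correlation near 0.9, inferred from an adult trial whose test is not stated. They are illustrative; the direction of the bias and the formula do not depend on them. The SAP model is itself biased towards zero under carryover, and its no-carryover expectation is stated only for the primary outcome. That qualifies the SAP model but does not favour a post-treatment covariate.

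Tables 8 and 9 list height and weight at no visit, so their absence at Visit 7 proves little for BMI SDS. Section 12.1.1 carries that point.

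**Conclusion.** The concern holds, as a minor point. The models conflict, the protocol's covariate has no scheduled period-2 measurement, and the only nearby stand-in is the adjustment that SAP 6.3 rejects. With that stand-in and no carryover, a non-zero HbA1c effect is overstated by 14–19%, 35–40% and 45–47% at assumed correlations of 0.3, 0.7 and 0.9. Interval coverage falls to 93%, 78–82% and 41–49%. With carryover the protocol's bias shrinks and can reverse, while the SAP model is attenuated.

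The harm arises only if 14.3 is followed, and it falls mainly on the estimate and interval. The chance of passing the HbA1c step is nearly the same under both models. The primary endpoint and its sample size (65 evaluable, 72 randomised) are untouched.

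**What to change.** In protocol 14.3, delete the sentence on adjusting for the start-of-period baseline and the sentence limiting the model to two time points. Replace them with the SAP model:
- three records per child (pre-randomisation baseline, period 1, period 2), with baseline as its own time point;
- fixed effects for treatment and period, and a random effect for site (which reaches HbA1c and BMI SDS only through SAP 15.4);
- correlated records within child;
- no period-2 baseline covariate.

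State that this single model decides the HbA1c step of the fixed sequence, and record when it was fixed. The rank-transformation sentence already in 14.3 can stay.

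The cost is wording in 14.3 only, with no new data, visits or participants. If the change is classed as a substantial amendment, protocol section 18 requires ethics and regulatory approval.

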## **14.4 Extension Phase Analyses**

### **14.4.1 Primary Endpoint Analysis**

The primary analysis will evaluate the difference in time spent in the target glucose range, between 3.9 to 10.0 mmol/l (70 to 180 mg/dl) as recorded by CGM, over 18

months from the end of the primary phase, as compared to sensor augmented pump therapy during the primary study phase.

Mean  $\pm$  SD or summary statistics appropriate to the distribution will be reported for the primary endpoint for the sensor augmented pump phase of the main study and over the extension period. During the extension period, the primary outcome will be calculated by pooling all CGM readings occurring throughout the entire extension phase. This will include all readings from the day after the last visit of the main study up until the final day of the extension phase. A paired t-test will be used to compare values using sensor augmented pump to values during the extension phase. If the outcome is skewed, then a nonparametric test will be used instead.

However, previous experience suggests that the primary endpoint will follow an approximately normal distribution. Analyses will include individuals with at least 168 hours (1 week) of CGM data during the sensor augmented pump phase and at least 672 hours (4 weeks) of CGM data during the extension phase

A detailed analysis plan will be provided separately.

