## **5.6 Extension Phase Objectives (UK sites only)**

The objective of the extension phase is to evaluate the long-term efficacy of closed loop insulin delivery in maintaining glucose levels in the target range of 3.9 to 10.0 mmol/l (70 to 180 mg/dl) over 18 months from the end of the primary phase, as compared to sensor augmented pump therapy during the primary study phase.

The extension phase will also examine the effect of hybrid closed loop on glucose control, comparing HbA1c and parameters based on continuous glucose monitoring (CGM) to primary phase sensor augmented pump therapy.

The safety of hybrid closed loop glucose control will be evaluated in terms of episodes of severe hypoglycaemia and other adverse events.

The frequency and duration of use of the automated closed loop system will be assessed.

Emotional and behavioural characteristics of parents/guardians and their response to the closed loop system and clinical trial will be evaluated using questionnaires.

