## 10.8 Extension Phase Outcomes (UK sites only)

### 10.8.1 Primary endpoint and key endpoints

The primary endpoint is the difference in time spent with sensor glucose levels between 3.9 to 10.0 mmol/l (70 to 180 mg/dl) during the 18 months extension phase, as compared to sensor augmented pump therapy during the primary phase.

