86            ○ Emotional Problems Subscale  
87            ○ Conduct Problems Subscale  
88            ○ Hyperactivity Subscale  
89            ○ Peer Problems Subscale  
90            ○ Prosocial Subscale  
91            ○ Total Difficulties Score

92       13) Hypoglycemia Fear Survey  
93            ○ Behavior Subscale  
94            ○ Worry Subscale

95       14) WHO-5

96       15) Epworth Sleepiness Scale

97       16) Pittsburgh Sleep Quality Index  
98            ○ Subjective Sleep Quality Subscale  
99            ○ Sleep Latency Subscale  
100           ○ Sleep Duration Subscale  
101           ○ Habitual Sleep Efficiency Subscale  
102           ○ Sleep Disturbances Subscale  
103           ○ Use of Sleeping Medication Subscale  
104           ○ Daytime Dysfunction Subscale

105       17) Children's Sleep Habit Questionnaire  
106           ○ Bedtime Resistance Subscale  
107           ○ Sleep Onset Delay Subscale  
108           ○ Sleep Duration Subscale  
109           ○ Sleep Anxiety Subscale  
110           ○ Night Waking Subscale  
111           ○ Parasomnias Subscale  
112           ○ Sleep Disordered Breathing Subscale

113                   ○ Daytime Sleepiness Subscale

114   All metrics listed above will be outcomes in the main study. In the extension phase, the same  
115   outcomes will be analyzed, with the exceptions of the Pittsburgh Sleep Quality Index and the  
116   Children's Sleep Habit Questionnaire. The primary outcome in the extension phase will be time  
117   in range calculated over the full 18 months.

118   **4.1 Calculation of CGM Metrics**

119   For the primary outcome and all secondary CGM metrics, a single value will be calculated for  
120   each subject for each period by pooling all CGM readings between the treatment initiation visit  
121   and up to 112 days post-initiation visit or the end of treatment visit, whichever comes first. All  
122   glucose sensor readings will be weighted equally in the pooled percentages regardless of how  
123   they distribute across weeks. Data will not be truncated due to protocol deviations.

124   Baseline CGM metrics will be calculated by pooling all readings up to the last 14 available days  
125   of CGM readings prior to randomization.

126   In the extension phase, CGM metrics will be calculated by pooling all readings inclusively  
127   occurring from the day after the last visit of the main study up until the last visit of the extension  
128   phase.

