129   Additionally, CGM metrics will be calculated every three months during the extension phase by  
130   inclusively pooling all CGM readings falling within each of the windows specified at each month  
131   in the table below:

Month	Window for Analysis
Month 3	Days 1-91
Month 6	Days 92-182
Month 9	Days 183-274
Month 12	Days 275-365
Month 15	Days 366-456
Month 18	Days 457-548

132

133   **4.2 Calculation of BMI SD Scores**

134   BMI standard deviation score will be calculated using the WHO growth chart.

135   **5. Analysis Datasets and Sensitivity Analyses**

136   **5.1 Analysis Cohorts**

- 137   • The primary analysis and all secondary analyses will be performed on a modified  
138   intention-to-treat basis with each day included in the treatment group assigned by  
139   randomization.
- 140   • A per-protocol analysis restricted to randomized participants with a minimum of 60% of  
141   available CGM readings during the control period and 60% CL system use during the CL  
142   period will be conducted for the primary outcome.
- 143   • Safety outcomes will be reported for all enrolled participants, regardless of whether the  
144   study was completed.

145 **6. Analysis of the Primary Efficacy Endpoint**

146 **6.1 Included Subjects**

147 In analyses conducted in the main study, only subjects with at least 168 hours of CGM data in at  
148 least one period will be included. If a subject has more than 168 hours of data in period 1 and  
149 then drops out of the study without any data in period 2, then he or she will be included in the  
150 analysis.

151 In the extension phase, analyses will include participants with at least 168 hours of CGM data  
152 during the SAP phase of the main study and at least 672 hours of CGM data during the extension  
153 phase. For the analyses conducted every three months during the extension phase, at least 168  
154 hours of CGM data will be required within a given three-month period to be included in the  
155 tabulations of summary statistics for that particular period.

156 **6.2 Missing Data**

157 Missing data will not be imputed for the primary analysis in this study.

158 **6.3 Statistical Methods**

159 Mean  $\pm$  SD or summary statistics appropriate to the distribution will be reported for the primary  
160 outcome and each of the key secondary outcomes listed below over the four month period by  

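### The extension's primary time-in-range outcome is labelled as covering 18 months, but four weeks of readings from anywhere suffice, and time in range late in the extension is never tested

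*Combined protocol and SAP*

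**What the plan says.** SAP here means the statistical analysis plan; the comparator is written out as sensor-augmented pump.

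- **Objective.** Protocol 5.6 sets out "to evaluate the long-term efficacy of closed loop insulin delivery in maintaining glucose levels in the target range" over 18 months. Protocol 10.8.1 defines the endpoint as time in range "during the 18 months extension phase, as compared to sensor augmented pump therapy during the primary phase".
- **Label.** SAP section 4 describes the extension primary outcome as time "in range calculated over the full 18 months".
- **Construction.** Protocol 14.4.1 states that "the primary outcome will be calculated by pooling all CGM readings occurring throughout the entire extension phase". SAP 4.1 does the same, from the day after the last main-study visit to the last extension visit.
- **Inclusion.** Protocol 14.4.1: "Analyses will include individuals with at least 168 hours (1 week) of CGM data during the sensor augmented pump phase and at least 672 hours" in the extension. SAP 6.1 repeats the rule, asking for 168 hours "during the SAP phase of the main study and at least 672 hours of CGM data during the extension" phase. Neither document says where in the 18 months the 672 hours must fall.
- **Test.** "A paired t-test will be used to compare values using sensor augmented pump to values during the extension phase" (protocol 14.4.1; also SAP 6.3), with a nonparametric test if the outcome is skewed. No weighting by amount of data is described.
- **Missing data.** "Missing data will not be imputed for the primary analysis in this study" (SAP 6.2).
- **Three-month windows.** SAP 4.1 defines six windows, the last being Days 457-548, and SAP 6.1 requires 168 hours in a window. Protocol 14.4.2 and SAP 7.4.1 use them for summary statistics only.

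**The concern.** The label promises an average over 18 months. The estimator gives the average over whatever time each child was observed, then averages children with equal weight. A child who stops supplying data after five weeks contributes a value for weeks 1 to 5 that counts as much as a completer's 18-month value. A child who wears sensors heavily at first and little later is weighted towards the early months.

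Uneven coverage is plausible. Protocol 9.19 lists CGM among the items supplied for the primary phase, but for the extension only the app, phone and pump. Protocol 9.15 speaks of retaining children who stop the intervention, but it sets no CGM requirement for them in the extension and invites withdrawn children only for an HbA1c sample.

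At stake is whether the primary result can be read as a statement about 18 months. It also matters that nothing planned tests the primary measure near the end, when durability would show.

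**Working it through.** **1. The threshold.** 672 / 24 = 28 days, which agrees with the protocol's 4 weeks. The windows have 91, 91, 92, 91, 91 and 92 days, 548 in all. Coverage at the minimum is 672 / (548 × 24) = 672 / 13,152 = 5.1%.

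**2. Weighting.** With one value per child and an unweighted test, a child with 28 full days and a child with 548 full days count equally. Each reading of the first child therefore carries 548 / 28 = 19.6 times the weight.

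**3. When this causes bias.** Let *f* be the share who leave early, *E* the gain over sensor-augmented pump averaged over the leavers' observed time, and *A* the average gain over all 18 months. If completers wear sensors evenly and leavers would have followed the same course, the plan estimates (1 − *f*)*A* + *fE*. The error is *f*(*E* − *A*). It is zero if *f* = 0 or if the gain is constant (*E* = *A*). It is positive if the gain wanes and negative if it grows.

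**4. Size (assumed inputs).** The documents give no extension attrition and no time trend. Assume the gain falls in equal steps across the six windows and leavers go after the first window, so *E* = 8.

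| Leavers | Gain 8 to 4 (*A* = 6.0) | Error | Gain 8 to 2 (*A* = 5.0) | Error |
|---|---|---|---|---|
| 10% | 0.9 × 6 + 0.1 × 8 = 6.2 | 0.2 | 0.9 × 5 + 0.1 × 8 = 5.3 | 0.3 |
| 20% | 0.8 × 6 + 0.2 × 8 = 6.4 | 0.4 | 0.8 × 5 + 0.2 × 8 = 5.6 | 0.6 |
| 40% | 0.6 × 6 + 0.4 × 8 = 6.8 | 0.8 | 0.6 × 5 + 0.4 × 8 = 6.2 | 1.2 |
| Gain in the last window | 4.0 | | 2.0 | |

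For leaving exactly at the threshold, assume a linear fall from 5 to 0 over 548 days (*A* = 2.5). A 28-day leaver then has *E* = 5 − 5 × 14 / 548 = 4.87. The plan gives 2.74, 2.97 and 3.21 with 10%, 20% and 30% leavers.

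**5. Against sampling error.** Two UK sites at 8-12 children each give 16-24 at most; take 20. With the main-study SD of 10.3 and correlation of 0.3 (protocol 14.12), the SD of a paired difference is 10.3 × √(2 × 0.7) = 12.2, and the standard error is 12.2 / √20 = 2.7 points. If the gain varies between children with an SD of only 4 (assumed), it is 4 / √20 = 0.9.

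**6. Tests late in the extension.** Protocol 14.4.2 lists HbA1c at 18 months and says HbA1c analysis parallels the primary one; SAP 13.2 gives it an adjusted p-value. For time in range there is only the pooled comparison.

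**The case against.** The strongest reply is that protocol and SAP agree on a prespecified rule, that equal weighting of readings follows the main study, and that a low threshold avoids restricting the analysis to completers. This stands, and it is a good reason to keep the pooled test.

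The planned report would also show much of the problem. The six windows would display waning, SAP 9.2 plans a visit flow chart, and protocol 14.6 tabulates closed-loop use in the extension. This stands in part: the window tables are descriptive, and their denominators change as children leave. The 60% per-protocol analysis is defined for the main-study periods only, and no sensitivity analysis for extension dropout is planned.

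The error may be small. At 10%, the only dropout figure in the documents and a main-study one, the 8-to-4 scenario is off by 0.2 points, well inside either standard error above. That stands too.

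A reader might go further and infer three things that the documents do not support:

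- *That an early-weeks effect will be reported as long-term efficacy.* This needs both uneven coverage and a changing effect, and the documents establish neither. Eligible children use sensor-augmented pumps as standard care, so some who stop closed loop may keep producing readings, although the plan does not require it.
- *That nothing is tested at month 18.* HbA1c is, as an exploratory endpoint.
- *That the primary analysis should be replaced by a repeated-measures model.* A sensor-augmented pump value plus six windows makes seven time points, and an unstructured covariance then has 7 × 8 / 2 = 28 parameters, for 16-24 children or fewer. Such a model can itself be biased when poor responders leave selectively.

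**Conclusion.** The mismatch between label and estimator is real and appears in both documents: the outcome is called 18-month time in range but is an average over the time observed, with 5.1% coverage sufficient. Whether it biases the result is conditional. It does so only if some children leave early or wear sensors mainly early, and the effect also changes over time. Under the assumed falls from 8 points, the error is 0.2 to 0.8 (to 4 points) or 0.3 to 1.2 (to 2 points) for 10% to 40% leavers. These sizes rest on assumed waning, assumed leaving after the first window, and leavers who would have followed the same course.

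The gap that does not depend on those assumptions is that no planned test addresses time in range, the primary measure, late in the extension. This calls for a cheap addition. It does not invalidate the planned analysis.

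**What to change.** Keep the pooled paired t-test as primary. In protocol 14.4.1 and SAP 6.3, prespecify two supportive comparisons with the sensor-augmented pump period, using the SAP 4.1 windows and the existing 168-hour minimum:

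- (a) the Days 457-548 window minus sensor-augmented pump, as the named long-term time-in-range contrast;
- (b) the equal-weight average of the six windows minus sensor-augmented pump, from a repeated-measures model with a simple covariance structure, stated in advance and suited to the small sample.

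Report the number of children contributing to each window. If the pooled result differs from (b), describe it as an average over the time observed.

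The cost is a wording change and a little more analysis, since the window values are already to be computed. On the documents' dates (SAP version 3.0 in May 2021, last extension participant expected in October 2022) it could be settled before the extension data were complete. The limits should be stated: (a) rests on children still supplying data, and (b) assumes data are missing at random and can be slightly biased if poor responders leave selectively.
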